## **REVIEW OF LITERATURE**

Warts are common skin conditions resulting from infection of keratinocytes by human papillomavirus (HPV). The development of epidermal thickening and hyperkeratinization occurs following infection at the basal layer and clonal proliferation, which eventually results in a visible wart, weeks or even months later.

Many studies have documented the prevalence of cutaneous warts in children 9– 13, ranging widely from 3.3% in the USA to 33% in the Netherlands. In a study conducted by. Liu et al it was found that 1.4% of college students were affected with warts on their hands and/or feet.  This frequency is estimated to be 7 to 10% of the population in Europe and in the United States. According to age group, the prevalence of warts is highest in school-aged children, followed by adults then preschool-aged children.  In Great Britain, 6.5% of the school children had plantar warts, and 9.5% had warts at other sites.

Most large studies have found no evidence of a sex difference in wart prevalence. However, a female preponderance is seen in the frequency of plantar warts. In the East Anglia survey, 8.4% of females had plantar warts compared to 4.9% of males.

The use of swimming pools, sports clubs, gymnasiums, or public baths increases the risk of contracting plantar warts. School children and young adults constitute a high epidemiologic risk population and an important source of the dissemination of cutaneous warts since their families are more often infected up to 50% of cases.

Among butchers and workers in the meat-handling industry, the prevalence of warts on the hands is much higher than in the general population as their hands are subjected to many traumatisms. Other factors thought to be responsible are cold, permanently humid conditions, in which workers often use the same tools and working tables.

# Classification of warts

Cutaneous warts can be classified in relation to the clinical morphology and the type of infecting HPV as follows:

- 1. Common wart (Verruca Vulgaris)
  - a. typical or exophytic
  - b. mosaic
  - c. endophytic,
  - d. papillomatous or filiform
- 2. Plane and intermediate warts
- 3. Myrmecia
- 4. Pigmented plaques
  - 1. Typical common warts are exophytic, i.e. elevated. Their surface is rough irregular, hyperkeratotic, with minute papillary projections.
  - 2. Mosaic warts appear usually in plantar locations. They are superficial, only slightly raised above the skin level, hyperkeratotic, multiple, confluent with polygonal outlines, and painless.

- 3. Endophytic common warts appear characteristically in palmar and plantar localizations. Deep plantar common warts are most often multiple, painless, with a slightly raised, hyperkeratotic surface. Even for experienced dermatologists, the differentiation between myrmecias and deep common warts is difficult.
- 4. Papillomatous common warts are usually less typical, resembling papillomas, localized most often on the face, head, neck, in the folds.
- 5. Plane warts are slightly raised above the skin level, smaller than common warts, with flatter, smoother surfaces and irregular outline. Intermediate warts, a term applied to lesions that cannot be classified as common or plane warts, combine clinical features of both.
- 6. Myrmecia warts, if in plantar location, are often referred to as deep plantar warts. They may also be palmar and the warts are endophytic, deep, and more often single. Characteristic findings include small bleeding points and punctate dots appearing after trimming off the hard horny covering.

A few atypical warts, example, pigmented plaques in immunosuppressed patients, remain unclassified until more is known about the incidence and natural history.

### Intralesional MMR vaccine

The mechanism of action of intralesional MMR immunotherapy is still an enigma. Some authors hypothesize that it acts through the induction of a strong nonspecific inflammatory response against the HPV-infected cells. It has also been suggested that the trauma itself may cause wart clearance in previously sensitized individuals. The cytokines produced by immune system such as interleukin (IL)-2, IL-4, IL-5, IL-8, interferon (IFN)- $\gamma$  and tumor necrosis factor (TNF)- $\alpha$  stimulate a strong immune response against HPV may be another possible mechanism of action. Another author reports that the response to antigen injection was associated with the proliferation of peripheral blood mononuclear cells that promotes Th1 cytokines including IFN- $\gamma$  and IL 2, which further activate cytotoxic T cells and natural killer (NK) cells that eradicate HPV-infected cells.

Subjects can be tested for existing immunity by intrademal injection of 0.1 mL of MMR vaccine into the skin of the forearm. Determination of a positive reaction requires erythema and induration of at least 5 mm in diameter within 48–72 hours. Patients reactive to the skin test are labelled responders and IL MMR is more effective in them.

**Nofal A et al** conducted a randomized controlled trial (RCT) with 135 patients of which 85 patients received the MMR vaccine and 50 received Normal saline as control. Both treatment groups were injected in single largest wart at 2 weekly intervals until complete clearance for a maximum of 5 treatment and were followed up bimonthly for 6 months. In the MMR group, complete response was achieved in 80% and 84.6% of patients presenting with recalcitrant and multiple warts respectively. No recurrence was observed in the MMR group and side effects included pain during injection and flu-like symptoms.

Author	Setting	Type of	Sample	Type of	Percentage of
		Study	size	wart	complete clearance
Nofal A and	Zagazig University,	Randomize	135	Common	Recalcitrant wart-
Nofal E,	Egypt	d controlled		warts	80%
2010 		trial			Multiple Wart-84.6%
Nofal A et al.	Zagazig University,	Prospective	65	recalcitran	63%
2015 	Egypt			t wart	
Naseem R	Federal	Prospective	170	Common	81.3%
and Aamir S,	postgraduate			warts	
2013 	medical Institute &				
	Sheikh Zayed				
	Hospital, Lahore,				
	Pakistan				
Mohamad	Alexandria Main	Quasi	100	Plantar	82%
NS et al,	University Hospital,	experimenta		wart	
2013 	Egypt	l trial			
Shah A et al,	NHL Municipal	Prospective	50	Common	72%
2016 	Medical College,	study		warts	
	Ahmedabad,				
	Gujarat, India				
Raju J et al,	Mysore Medical	Prospective	27	Common	70.4%
2016 	College &	study		warts	
	Research Institute,				
	Mysore, India	-			
Rohit V et al,	Chalmeda Anand	Case-	50	Common	72%
2017**	Rao Institute of	control		warts	
	Medical Sciences,	study			
	Telangana, India.				22.424
Chauhan PS	Dr.R.P. Govt.	Prospective	51	Common	82.4%
et al, 2017 	Medical College,	study		warts	
	Kangra (Tanda),				
	Himachal Pradesh,				
	India				

Table 1: Comparison of different studies on IL MMR in warts

Again in 2015, **Nofal et al** conducted a similar study in recalcitrant wart where they included sixty-five patients. Recalcitrant warts were defined as warts persistent for more than two years despite treatment with at least two different modalities. Distant warts were defined as warts at different anatomic sites away from the treated wart. Complete clearance of the lesions was observed in 41 patients (63%), partial response in 15 patients (23%), and no response in nine patients (14%). Complete response was demonstrated in 74.5% of those presenting with distant warts. Side effects were mild and insignificant in the form of pain during injection, itching, erythema, and edema at the site of injection and flu-like symptoms. Recurrence was detected in two patients only

Similarly in a study conducted by **Naseem, Aamir** in 2013 there were total 170 patients and final efficacy came as 81.3% which shows that a large number (122) of patients show complete response to the MMR vaccination.

**Nagat Sobhy Mohamad, et al** observed that the response of the target wart, MMR- treated group showed a significantly higher rate of complete clearance compared with the control group (82% versus 0% respectively). The rate of partial response was 6% versus 30%, and the rate of no response was 12% versus 70%, respectively. Regarding the response of untreated distant warts, the MMR-treated group showed 86.9% complete and 13.1% partial clearance of the warts whereas the control group showed 100% no response.

In a prospective study conducted in the Dermatology outpatient department of V.S Hospital, Ahmedabad by **Shah A et al** over a period of one year patients received

intralesional MMR vaccine 0.5ml into a single wart or the largest wart in case of multiple lesions at an interval of two weeks for three treatments. The response was evaluated as 0-49% as no response, 50-99% as partial response and 100% as complete response. Follow up was made every 02 weeks for 06 weeks and then monthly for 06 months to detect any recurrence. They found complete response was seen in 36 (72%), partial response in 08 (16%) and no response in 06 (12%) patients. No recurrence was observed. Pain at the site of injection in 18 (36%) and the flu like symptoms in 02 (04%) patients were observed. 

In 2016 **J Raju et al** injected MMR vaccine into the largest single wart intralesionally and gave subsequent injections every 2 weeks apart for about 3 to 5 times and obtained complete remission of warts in 70.4% of patients, partial remission in 22.2% and no response in 7.4% of patients. 

**Vontela R et al** observed complete clearance in 72% patients and partial clearance in 16% of patients receiving the MMR vaccine. No response is seen in 12% of patients. The recurrence rate during the 6 months follow up period is 12%. Pain during injection was noted in 60% of patients without any other adverse effects in the treated patients. The mean duration taken to show the complete clearance of the lesions is 9 weeks

In 2017 **Chauhan et al** injected 0.25 mL MMR vaccine intralesionally in the largest wart and repeated at 2-week interval until complete clearance or a maximum of five doses. They evaluated outcome as complete clearance, excellent, good, or unsatisfactory response on a visual analog scale at every visit

and at 4 and 8 weeks, thereafter by comparing baseline clinical photographs. They used a Likert scale for patient satisfaction level assessment similarly. Out of 51 patients who completed the study 42 (82.4%) of them showed complete clearance of warts and 9 (17.6%) patients showed good or unsatisfactory response. In 4 (7.8%) patients, warts subsided completely after one dose itself. The four patients showing an excellent response after five doses initially also continued to improve during a follow-up period of 8 weeks. Except for injection site pain, no adverse effects were noted. There was no recurrence of warts among them.

### **Intralesional Vitamin D3**

Vitamin D3 acts on the principle of immunotherapy by stimulating cell-mediated immunity Vitamin D is also claimed to regulate epidermal cell differentiation and proliferation and may modulate cytokine production through its action upon vitamin D receptors. The vitamin D receptors are present in the keratinocytes, melanocytes, fibroblasts, and immune system cells of the skin. Activation of Toll-like receptor (TLR) of human macrophages up-regulates the expression of vitamin D receptor and vitamin D1- hydroxylase genes, leading to induction of the antimicrobial peptide  like thymic stromal, lymphopoietin and cathelecidin. It also reduces the synthesis of IL 1a and IL6 resulting in decreased inflammation. VDR activators (VDRAs) have been shown to inhibit cell replication and have immunomodulatory properties.

Author	Setting	Type of study	Sample size	Type of wart	Percentage of complete clearance	Recurre nce
Aktaş et al. 2016 	Different hospitals of Turkey	Prospective study	20	Common warts	80%	No
Jakhar, Kaur, and Misri 2018 	NDMC Medical College and Hindu Rao Hospital, Delhi	case report	1	Periungal wart	-	Not mentione d
Raghukumar et al. 2017 	Hassan Institute of Medical Sciences, Hassan, Karnataka state, India	Prospective study	64	recalcitrant warts	90%	2(3.7%)
Kareem et al. 2019 	Al-Azhar University, Cairo, Egypt	RCT	50	Common warts	40%	Not mentione d
El-Taweel, Salem, and Allam 2019 	Benha University, Egypt	Prospective study	20	Common warts	40%	No
Manjunath K et al. 2019 	Mandya Institute of Medical Sciences, Mandya, Karnataka, India	Prospective study	42	Multiple warts	78.57%	1(5.26%)

Table no. 2: Comparison of studies on IL Vitamin D3 in Warts

**Aktas et al** conducted study with 20 patients with single or multiple plantar warts. Vitamin D3 (0.2 mL, 7.5 mg/mL) was injected into the base of the warts after prilocaine (0.1 mL, 20 mg/mL) injection. A maximum of 5 warts were treated in 1 session, with a maximum 2 injections performed at 4-week intervals. In total, 16 of 20 patients (80%) showed complete resolution of warts, and 1 patient showed partial resolution. Three patients failed to show any response. No recurrence or serious adverse effects were observed. 

In a case report done by **Jakhar, Kaur, and Misri** in 2018, the injection was given at a dose of 0.1 mL/cm2 just beneath the wart. A maximum of 0.4 mL was used in a single session in cases of multiple warts. The session was repeated at 2-week intervals for a maximum of 4 sessions or complete resolution of warts, whichever is earlier. The resolution of warts typically started in 7 to 10 days, and warts are shed spontaneously within 4 to 6 weeks. The only side effect was pain during injection, which was minimized with a dose of lidocaine before injection with vitamin D3. Two to 4 sessions are usually required on average for complete cure.

**Raghukumar et al.** conducted a study in 2017 in 64 patients with recalcitrant warts. Complete response with IL vitamin D was seen in 54 of 60 (90%), partial response in 4 of 60 (6.66%), and no response in 2 of 60 (3.33%). The average number of injections required to achieve a complete resolution was 3.66. Complete resolution of distant warts was noticed in all patients.

**Kareem et al.** conducted RCT in 50 patients who were divided into two groups: thirty patients as cases group who received an intralesional injection of 0.2 ml of vitamin D3 (300.000 IU) and another twenty patients as a control group who were injected with normal saline solution. Standardized photographs were taken before, one month and three months after the procedure. The degree of the response was classified into complete, partial and no response. Complete clearance of the target injected warts was seen in 40% of patients in the cases group and 5% of patients in the control group (P≤0.001) that was statistically significant.

Similarly, in a study conducted by **EI-Taweel et al.** 20 patients with verruca vulgaris and deep palmoplantar warts were included. Forty percent of the lesions treated with IL vitamin D3 showed complete clearance and the rate of distant wart response was 17.65%. Among different demographic and clinical variables in the studied patients, smoking and older age seemed to decrease the therapeutic response 

In a prospective study conducted by **Shilpa et al** on 2019, 33 of 42 patients (78.57%) showed a complete response, 6 patients (14.28%) showed moderate response and three patients (7.14%) showed mild response with IL vitamin D3. Recurrence was observed in one patient with the palmoplantar wart. No serious adverse effects were reported.

# **OBJECTIVES**

# **Primary Objectives:**

- 1. To determine the efficacy of IL MMR vaccine in the treatment of Wart
- 2. To determine the efficacy of IL vitamin D in the treatment of wart
- 3. To compare the efficacy of IL MMR vaccine and IL Vitamin D

# Secondary Objective:

- To determine the clinical and demographic profile of patients with different types of warts visiting Dermatology outpatient department of BPKIHS
- 2. To determine the side effects of IL MMR vaccine and IL Vitamin D in treatment of wart
- 3. To determine Dermatology life quality index (DLQI) in wart patients.

# **RESEARCH HYPOTHESIS**

# Null Hypotheses (H0):

IL MMR vaccine is not better than IL Vitamin D in the treatment of wart

# Alternative hypothesis:

IL MMR vaccine is better than IL Vitamin D in the treatment of wart

# **Operational definition**

Wart - clinical diagnosis made by a dermatologist

Grades of clinical	Definition	VAS
improvement		score
Complete response	Complete disappearance of warts including	100%
	distant ones and skin texture at the site is	
	restored to normal	
Excellent response	Reduction in size and number including distant	75–99%
	ones and few residual warts still visible	
Good response	Some reduction in size only including that of	50-74%
	distant ones but no decrease in number of	
	warts	
Poor or no response	No significant change in size and number of	0–49%
	warts	
Recurrence	Recurrence during the study period	

Table no. 3 : Patient and physician global assessment using visual analog scale

score

# MATERIALS AND METHODOLOGY

## Materials:

The study population will be all patients clinically diagnosed with warts visiting the Dermatology outpatient department of BPKIHS, Dharan.

# Study design:

A Prospective comparative longitudinal study

## **Study Period:**

The probable duration of the study will be one year after approval from the Institutional Review Committee and Nepal Health Research Council (NHRC)

### **Ethical Clearance**

Ethical clearance will be taken from Institutional Review Committee (IRC), BPKIHS and Nepal Health Research Council (NHRC).

# Conflict of interest: None

**Sampling Technique:** Census method with all consecutive patients meeting inclusion criteria for initial 6 months

### **Inclusion criteria**

- 1. Clinically diagnosed patients who have more than three warts or single wart in difficult to treat sites (periungual, palms and soles)
- 2. Age >/= 12 years

### **Exclusion criteria**

- 1. Patients under any systemic or topical treatment of warts for the last 4 weeks
- 2. Patients with a past history of an allergic response to MMR or any other vaccine or Vitamin D
- 3. Patients with current acute febrile illness or any bacterial infection
- 4. Immunosuppressed patients
- 5. Pregnant or lactating women
- 6. Patients having a past history of asthma, allergic skin disorders or convulsions
- 7. Patients with keloidal tendency
- 8. Patient refusal for consent
- 9. Treating physician's decision to give other modality of treatment
- 10. Patients with hypervitaminosis D, muscle weakness, bone pain, altered sensorium

### Sample size

The study considers a 95% confidence interval, 80% power to estimate sample size. According to the literature review, it was found that 84.6% and 40% improvement were seen with IL MMR and IL Vitamin D respectively.

Now using the sample size estimation formula for 2 proportion

```
Now using the sample size estimation formula for 2 proportion

n = 2p(1-p) (Z\beta + Z\alpha/2)^2
```

n= sample size for each group

 $p_1 = 0.846$ 

 $p_{2} = 0.40$   $p = (p_{1} + p_{2})/2$   $Z_{\alpha/2} = 1.96 \text{ at } 95\% \text{ CI}$   $Z_{\beta} = 0.842 \text{ at } 80\% \text{ power}$ Using above formula, n= 18.54 Considering loss of follow up, sample size in each group= 30 Total sample size= **60** 

### Methodology

Based on the computer generated random number table, patients will be assigned to either Group A or Group B once they come to OPD. Informed consent will be taken. After that detailed information of all the patients satisfying inclusion criteria will be recorded in preset pro forma. This will include personal data, past history, medical history, drug history, clinical data like site, size, number, distribution of lesions. History of muscle weakness, bone pain, altered sensorium, anaphylaxis and immunosuppression will also be taken. In patients of group B serum vitamin D level will be measured after 20 days of 3rd dose and 1 month after the last dose to ensure safe monitoring. Photographs of the lesions will be taken before the first treatment session, in every treatment session and 3 months after last session.

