#### Statistical analysis

- Data handling: Data will be entered in Microsoft Excel 2010 (Microsoft Corporation, Redmond, Washington, USA) and statistical analysis will be done using Statistical Package for the Social Sciences 10.5 version (Chicago, Inc)
- 2. Coding: Alpha numerical code will be used
- Monitoring: Data will be entered after every day of work and supervised by guide.
- 4. Statistical analysis will be conducted as per both per-protocol and intention-to treat population (defined as all enrolled patients to whom study drug will be given; with the last observation carried forward) basis using two sided tests.

For *descriptive statistics*, percentage, mean, S.D., median, and minimum, maximum will be calculated along with graphical and tabular presentation.

For inferential statistics, statistical methods that will be used are as follow

- a. Chi square test and Fisher's exact test to compare the categorical data between the groups.
- b. Paired t test for comparing normally distributed continuous variables (pretreatment and post treatment DLQI) at different time point within the groups.
- c. Mann- Whitney U test to compare the not normally distributed variables (age, duration of illness, size, number)
- d. Kaplan–Meier curves to compare the response rate (complete, excellent, good or poor response) on each follow up visit (week 3, 6, 9, 12) between the groups.

Test of significance will be considered when value of  $p \le 0.05$ .

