# ANNEXURES

### Department of Dermatology and Venereology

### **BPKIHS**, Dharan

### Proforma for Wart patients

SN:	Group:	OPD/Inpatient no:	Date:			
Name	e					
Age (years): Sex:						
Race/ethnicity:						
Education:		Occupation:				
Address:		Phone no.				
History:						
1) Duration of w	art:	2) Type of wart:				
3) Site	of lesions:	Scalp/Face/Neck/Trunk/Upper	extremities/Lower			
Extremities/Palr	ns/soles/finger/toes					
4) Number of Le	sions at presentatior	1:				
5) Size of lesion:						
6) Progression o	f lesion: Gradual/Rap	bid/Stable/ Regressing				
7) Any associate	d Symptoms:					
	Pruritus: none/ mild,	/ moderate/ severe				
	Pain: none/ mild/ mo	oderate/ severe				
	Burning sensation: n	one/ mild/ moderate/ severe				
8) Associated pe	rsonal Systemic illne	ss: Yes/No				
If yes: HIV/ Diab	etes/ Asthma/ Allerg	ic skin disorders/ Convulsion/ bone	pain/ muscle weakness			
9) Pregnant/ lac	tating mother: Yes/N	Io/ NA				
10) Taking any o	ther drugs: Yes/No					
If yes: Corticoste	eroids/ Immunosupp	ressive/ Others				
11) Past treatme	ent taken: Yes/ No					
If yes: Self-ca	re (Herbs/ Drugs/ Bo	ught from pharmacy)				
Traditio	nal (Traditional beak	ar/Herbalist/Other)				
Fractional (Fractional nealer/ Herbalist/ Other)						
Improve	Seek medical help or treatment (Topical/ Systemic/ Both/ Surgical)					
Timo cin	anent. worse/ NO/ N					
Time Sin						

Reason for treatment:

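### As written, the arm is assigned before consent and exclusion-relevant history, with no concealment described, and the intention-to-treat set contains only dosed patients

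*Combined protocol and SAP*

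**What the plan says.** **Order of steps.** The Methodology section opens with a computer-generated random number table and states that "patients will be assigned to either Group A or Group B once they come to OPD. Informed consent will be taken". It continues: "After that detailed information of all the patients satisfying inclusion criteria will be recorded in preset pro forma". In the same step, "History of muscle weakness, bone pain, altered sensorium, anaphylaxis and immunosuppression will also be taken".

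**Who is approached.** The Sampling Technique line reads "Census method with all consecutive patients meeting inclusion criteria for initial 6 months". It mentions inclusion criteria but not exclusions or consent.

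**Exclusions that can act late.** Item 8 of the Exclusion criteria is "Patient refusal for consent". Item 9 is the treating physician's "decision to give other modality of treatment", with no criteria attached.

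**Concealment.** Only the generation of the sequence is described. There is no mention of envelopes, central allocation, a custodian of the list or blinding. The alphanumeric code in the statistical section is listed with data handling and is not an allocation procedure.

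**Analysis set.** Item 4 of the Statistical analysis section, and item d of the statistical methods in the Summary, give the intention-to-treat population as "defined as all enrolled patients to whom study drug will be given", with last observation carried forward, beside a per-protocol analysis. The term enrolled is not defined.

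**The concern.** Randomisation protects the comparison only if nobody can act on the assignment before the patient is committed to the trial, and if everyone assigned is then accounted for. As written, neither is secured. Consent, eligibility and the physician's discretion all come after the arm could be known, and those who leave at that stage are in neither analysis set.

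The documents themselves give reasons why such exits might differ by arm:

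- **Price.** The Summary says that the patient pays. Its budget uses 350 per MMR session and 80 per vitamin D session, so five sessions cost 5 × 350 = 1,750 against 5 × 80 = 400 NRS for the drug. Investigation costs are not split by arm, so the net difference is unknown.
- **Arm-linked exclusions.** The Rationale ties the immunodeficiency exclusion to MMR and lists use in immunosuppressed patients as an advantage of vitamin D. Exclusion 10 begins with hypervitaminosis D. A clinician who knows the arm could apply these exclusions unevenly.
- **Discretion.** Exclusion 9 is open-ended.

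The third primary objective, the comparison of the two treatments, is what is at stake. As planned, a reader could not tell whether selective exits had occurred.

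**Working it through.** **1. Sequence against exclusions.**

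| Step as written | What it can reveal | Exclusion affected |
|---|---|---|
| Assignment on arrival | – | – |
| Consent | refusal | 8 |
| History listed in Methodology | immunosuppression; muscle weakness, bone pain, altered sensorium | 4, 10 |
| Annexure, "Proforma for Wart patients" (has a Group field) | pregnancy or lactation; asthma, allergic skin disorders, convulsions | 5, 6 |
| Any time before dosing | physician chooses another treatment | 9 |

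Each of these exits can follow assignment. None of these patients is dosed, so none is in the set called intention-to-treat, and the per-protocol set cannot recover them. Those who consented may have a form with a Group entry, but no analysis or report uses it.

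**2. The plan's own figure.** With p1 = 0.846, p2 = 0.40 and mean p = 0.623 (Sample size section):

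n = 2 × 0.623 × 0.377 × (1.96 + 0.842)² / 0.446² = 18.54 per group.

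This agrees with the plan, which then sets 30 per group. The point here is not a sample-size error.

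**3. Illustration of bias.** The documents give no rate of loss between assignment and first dose, so the following are assumptions:

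- 30 assigned per arm and true response 62.3% in both, so no real difference;
- a fraction f of one arm only is removed before dosing;
- those removed would have responded at rate r.

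Observed rate in the affected arm = (p − f·r)/(1 − f).

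- r = 0, f = 0.05: 0.623/0.95 = 65.58%, false difference 3.28 points.
- r = 0, f = 0.10: 0.623/0.90 = 69.22%, 6.92 points.
- r = 0, f = 0.20: 0.623/0.80 = 77.88%, 15.6 points.
- r = p/2 = 0.3115, same f: 63.94%, 65.76%, 70.09%, or 1.64, 3.46, 7.79 points.
- r = p: 0 points.

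**4. False-positive risk.** I enumerated all pairs of binomial outcomes with 28, 27 or 24 patients left in the affected arm against 30 in the other. Rejection is p ≤ 0.05, two-sided. The plan names both tests below without saying which applies to response.

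| Removed | Pearson chi-square, r = 0 | Chi-square, r = p/2 | Chi-square, r = p | Fisher, r = 0 | Fisher, r = p/2 |
|---|---|---|---|---|---|
| 5% | 6.0% | 5.4% | 5.1% | 4.4% | 3.8% |
| 10% | 8.6% | 6.1% | 5.3% | 5.8% | 3.8% |
| 20% | 24.6% | 9.8% | 5.5% | 19.7% | 6.9% |

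In the 5% row, 5% of 30 is 1.5 patients, so the enumeration uses 28 remaining, which strictly is 2/30 = 6.7% removed. Using f = 2/30 throughout with r = 0 gives 0.623/(28/30) = 66.75%, a false difference of 4.45 points and a chi-square risk of 6.7%. The conclusion does not change.

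**The case against.** The strongest reply is that the Methodology paragraph is loosely ordered prose. Its one explicit sequence marker places the data form after consent; nothing explicitly places consent after assignment. Both that paragraph and the Sampling Technique line presuppose that inclusion criteria are met. Refusal of consent and the physician's choice of another treatment are listed as exclusion criteria, which ordinarily act before entry. Writing a history on a form does not show that eligibility was first assessed then, and a Group field does not show when it is filled in. If enrolled means consented and eligible, and if the first injection follows at the same visit, the dosed set may lose almost nobody.

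The numbers can also be challenged. They require one-sided, prognosis-related removal. The 24.6% needs a fifth of one arm to leave, all of them non-responders. With Fisher's exact test there is little or no inflation above 5% at the smaller removal rates.

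Much of this stands as caution. Practice may be better than the text, the consent pages are not in the public copy, and the large figures are worst cases. It does not remove the point. Assignment first is the natural reading, and neither section places consent or the exclusions before it. The absence of a concealment procedure and the dosed-only analysis set do not depend on how that paragraph is parsed. A dosed-only set can be acceptable when allocation is concealed and exits do not depend on arm, but here the plan secures neither.

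**Conclusion.** The point holds as a reading of the plan as written. It should be fixed, with medium confidence about its practical effect. The text permits exits after a known assignment, and both analyses discard them without a trace. Whether bias results depends on exits being related to both arm and prognosis, which the documents cannot show; its direction is likewise unknown. Under the stated assumptions, the false difference runs from 0 to 15.6 points. It is at most about 3 points with 5% of one arm removed and becomes serious when about six of 30 leave one arm selectively. The figures illustrate what the plan leaves open and do not predict what will happen.

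**What to change.** 1. **Reorder the Methodology section.** Check all inclusion and exclusion criteria, including items 8 and 9; take consent; complete the baseline form; only then reveal the next concealed allocation. Sequentially numbered sealed envelopes made from the same random number table would serve.
2. **Redefine the analysis set** in the Summary and in the Statistical analysis section: intention-to-treat is all randomised patients in their assigned arm. Keep the dosed set as a supportive analysis, labelled modified intention-to-treat.
3. **Report** patients assigned but not dosed, by arm and reason.
4. **State in advance** how undosed patients are handled. Counting them as not cleared is one conservative rule, but it changes the estimand, so the dosed-set result should stand beside it.

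**Cost.** Rewording in three places, a set of envelopes, a short log and slightly more work at the first visit. No extra patients. If undosed patients count as not cleared, response rates fall and can differ between arms through non-treatment alone: 60% among 24 dosed of 30 becomes 0.60 × 24/30 = 48%. At the plan's 84.6% and 40% with 30 per arm, approximate power falls from 96.5% to 90.0% if 10% of both arms are undosed, and to 80.5% if 20% are. With concealed allocation after consent, few such patients should arise.
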